Medtronic Business Restricted

LINQ QT Study Clinical Investigation Plan						
21 SEP 2022	Version 2 Page 7 of 48			Medtronic		
	 Exclusion Criteria: Patients who have a contraindication to long-term antiarrhythmic therapy Patients not suitable for long-term antiarrhythmic therapy 					
	 Patients with a previo cardiac resynchroniza defibrillator (ICDs)) Co-enrollment in anoth during the course of the 	tion requir er study or p is clinical stu	ing > 40% pac blanning to partici	tion (i.e., cardi cing, implanta pate in a concu nfound the resu	ac pacemaker or ble cardioverter rrent device study lts	
Study Procedures and Assessments	Study Procedure	Baseline	Index Antiarrhythmic Loading Event	(Optional) 2, 4, 8 week	90-day Visit/Study Exit	
	Patient Informed Consent	Х				
	Inclusion/Exclusion Assessment	Х				
	Cardiovascular (CV) and Medical History	Х				
	Demographics	Х				
	Physical Exam	Х	Х	Х	X	
	Blood Labs	Х	Х	Х	X	
	CV Symptoms*optional	Х	Х	Х	X	
	Medications	Х	Х	Х	Х	
	12-Lead ECG	Х	Х	Х	Х	
	2D Echocardiogram*optional	Х				
	Holter/ VitalPatch [®] RTM		Х	Х	X	
	MyCareLink [®] Daily Manual Transmissions	Х	х	Х	X	
	Patient Activations		Х	Х	X	
Study exit X Serious, Cardiovascular- related Adverse Events X X					X	
		Х	X			
	Study deviations Report upon occurrence					
Safety Assessments	There are no defined safety end not to demonstrate safety or ef	ndpoints in the LINQ QT study as the purpose of the study is effectiveness. Cardiovascular-related (CV) adverse events that				

Medtronic Business Restricted

LINQ QT Stu	udy Clinical Investigation F	Plan			
21 SEP 2022	21 SEP 2022 Version 2 Page 8 of 48			Medtronic	
	result in hospitalization due to anti-arrhythmic loading will be collected throughout the duration of the subject's participation in the study, beginning after the initial in- hospital/out-patient anti-arrhythmic loading.				
Statistics	Since the study will be exploratory in nature and the study objectives are descriptive, no clinical endpoints will be developed. LINQ™/LINQII [™] derived data will be summarized using descriptive statistics.				

3. Introduction

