21 SEP 2022

Version 2

Page 30 of 48

10. Adverse Events and Complaint Reporting

All products used are approved, not investigational and the purpose of the LINQ QT study is not to demonstrate safety or effectiveness. Cardiovascular-related or serious adverse events that result in a hospitalization due to anti-arrhythmic loading will be collected throughout out the duration of the subject's participation in the study, beginning after the initial in-hospital/out-patient anti-arrhythmic loading. Deaths will not be collected unless it resulted in a CV-related hospitalization related to the anti-arrhythmic loading.

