10.1 Definitions/Classifications

For the purposes of clinical report, event definitions align with the International Organization for Standardization standard 14155 (ISO 14155). Where the definition indicates "device", it refers to any device used in the study. This might be the device under investigation, or any market released component of the system. For the purposes of the clinical report, Medtronic will classify each adverse event according to ISO 14155:2020 definitions. The study will follow the definitions, however, is not claiming full compliance to ISO 14155:2020.

General			
Adverse Event (AE)	Untoward medical occurrence, unintended disease or injury, or untoward clinical signs (including abnormal laboratory findings) in subjects, users or other persons, whether or not related to the investigational medical device and whether anticipated or unanticipated NOTE 1: This definition includes events related to the investigational medical device or the comparator. NOTE 2: This definition includes events related to the procedures involved. NOTE 3: For users or other persons, this definition is restricted to events related to investigational medical devices.		
	(ISO 14155:2020, 3.2)		
Relatedness			

Table 3: Adverse Event Definitions

Medtronic Business Restricted

21 SEP 2022	Version 2	Page 31 of 48	Medtronic
Cardiovascular Related	An adverse event relating to the heart and the blood vessels or the circulation (e.g., atrial fibrillation, myocardial infarction, stroke, peripheral vascular disease, heart failure).		
	Seriousness		
Serious Adverse Event (SAE) (ISO 14155)	Seriousness Adverse event that led to any of the following a) death, b) serious deterioration in the health of the subject, users, or other persons as defined by one or more of the following: 1) a life-threatening illness or injury, or 2) a permanent impairment of a body structure or a body function including chronic diseases, or 3) in-patient or prolonged hospitalization, or 4) medical or surgical intervention to prevent life- threatening illness or injury, or permanent impairment to a body structure or a body function, c) foetal distress, foetal death, a congenital abnormality, or birth defect including physical or mental impairment Note 1: Planned hospitalization for a pre-existing condition, or a procedure required by the CIP, without serious deterioration in health, is not considered a serious adverse event. (ISO 14155:2020, 3.45)		

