10.2 Reporting of Adverse Events

Cardiovascular-related, serious adverse events will be reported on the AE eCRF, including a description of the event, the diagnosis, the date of event onset, the date the site became aware of the event, the diagnostic tests and procedures performed, actions taken as a result of the event, and outcome of the event.

Documented pre-existing conditions are not considered AEs unless the nature or severity of the condition has worsened.

For all reportable events, initial reporting may be done by phone, fax, or on the CRF completing as much information as possible. The completed AE CRF must be submitted to Medtronic as soon as possible.

Medtronic Business Restricted

LINQ QT Study Clinical Investigation Plan				
21 SEP 2022	Version 2	Page 32 of 48		Mecttronic

For any changes in status of a previously reported adverse event (i.e., change in actions taken, change in outcome, change in relatedness), information needs to be updated on, or added to the original AE form. All AEs must be followed until the AE has been resolved, is unresolved with no further actions planned, the subject dies or exits the study, or study closure, whichever occurs first.

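### The protocol's passages on which adverse events are collected contradict each other, and the Section 10 sentence on deaths reverses cause and effect and conflicts with Section 10.2

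*Protocol*

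**What the plan says.** Four visible places state which events are in scope.

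- **Synopsis, Safety Assessments (prose).** "Cardiovascular-related (CV) adverse events that" "result in hospitalization due to anti-arrhythmic loading will be collected throughout the duration of the subject's participation in the study" (one sentence, split by a page break).
- **Synopsis, schedule of procedures (row label).** "Serious, Cardiovascular- related Adverse Events".
- **Section 10, opening paragraph.** "Cardiovascular-related or serious adverse events that result in a hospitalization due to anti-arrhythmic loading", with collection "beginning after the initial in-hospital/out-patient anti-arrhythmic loading".
- **Section 10.2.** "Cardiovascular-related, serious adverse events will be reported on the AE eCRF".

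Section 10 then gives a separate rule for deaths: "Deaths will not be collected unless it resulted in a CV-related hospitalization related to the anti-arrhythmic loading".

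Three definitions bear on these rules. Table 3 in Section 10.1 lists death as the first criterion for a serious adverse event, and also lists "in-patient or prolonged hospitalization". Table 3 limits hospitalization to a therapeutic inpatient stay of at least 24 hours. Table 4 in Section 10.2.1 sets out who classifies relatedness, seriousness and diagnosis. Its relatedness label describes events as arising from the loading hospitalization.

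**The concern.** These passages tell a site which events need an adverse-event form. If they differ, two sites that each follow the protocol can enter different events, and the final listing depends on which page was read. An analysis plan cannot repair this afterwards, because an event that was never entered cannot be recovered.

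The death sentence matters for a reason the protocol itself gives. Section 3.1 names sudden cardiac death as the harm to which QT prolongation can lead. If such a death occurs out of hospital, whether its diagnosis and relatedness are recorded beside the subject's QT data should not turn on which section governs.

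**Working it through.** No arithmetic is involved beyond counting. Each passage can be written as a condition on the event.

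| Place | CV-related? | Serious? | Loading-related hospitalization? |
|---|---|---|---|
| Synopsis prose | required | not mentioned | required |
| Synopsis row | required | required | not mentioned |
| Section 10 | either CV-related or serious | either CV-related or serious | required |
| Section 10.2 | required | required | not mentioned |

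The synopsis row and 10.2 agree. The other two differ from them and from each other. That makes three wordings in four places.

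Test cases, each passage taken as printed:

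| Event | Synopsis prose | Synopsis row | Section 10 | Section 10.2 |
|---|---|---|---|---|
| A. CV serious event, hospitalized because of loading | in | in | in | in |
| B. Non-CV serious event, hospitalized because of loading | out | out | in | out |
| C. CV serious event, no loading-related hospitalization | out | in | out | in |
| D. Sudden CV death out of hospital | out | in | out | in |

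Only case A has the same status everywhere. The mismatch runs both ways: Section 10 is wider than 10.2 in case B and narrower in case C. Case D is a special instance of C, shown separately because deaths have their own sentence.

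That sentence can be read in two ways.

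1. **Literal.** The death must have led to a hospitalization. A death cannot do that, so no death is ever collected.
2. **Repaired.** The death must have followed a CV-related hospitalization due to loading. A subject who dies suddenly at home has had no inpatient stay of 24 hours for that event, so case D is still excluded.

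On either reading Section 10 excludes case D. Yet the death makes the event serious under Table 3, and 10.2 asks for every CV-related serious event on the form.

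A secondary wording fault lies in Table 4. There the event arises from the loading hospitalization, whereas in Section 10 the event leads to a hospitalization.

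**The case against.** The best defence is that the protocol declares a narrow safety scope: there is no safety endpoint, and Section 5.2 says safety is not the main focus. That justifies a small event set. It does not justify a set whose membership changes between passages.

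Section 10.2 could also be read as operating inside the limits of Section 10. Case C then disappears and case D is excluded throughout. Case B remains, because Section 10 joins its two conditions with *or* while 10.2 joins them with *and*. The death sentence also remains defective.

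Deaths would not go wholly unrecorded. Section 8.12 requires the date and reason of exit on an eCRF, and Section 10.2.2 keeps local-law and IRB reporting in force. Both points stand, although neither supplies the event description and classification that 10.2 and Table 4 require. The content of Table 2 and of several procedure sections is not visible in the public text, so the point is confined to the passages that can be read.

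Some stronger readings are tempting, but the documents do not support them.

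- A reader might infer that every hospitalized event is serious, so that the CV limit in Section 10 does nothing. Note 1 to the Table 3 definition exempts planned admissions for a pre-existing condition, and procedures the protocol requires, where there is no serious deterioration. The inference therefore does not hold in general.
- A reader might infer that nothing in the protocol requires a diagnosis for a sudden out-of-hospital CV death. Section 10.2 as printed does require one. The fault is the contradiction with Section 10.
- A reader might count Table 4 as a further collection rule, or say that its label has no meaning after out-patient loading. Table 4 is a classification table, and its label may be shorthand for a later admission caused by loading.
- A reader might call the start of collection after loading an error, since the objective covers the loading period too. It is a declared choice, the same in both prose passages, and the objective concerns QT measurement.

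**Conclusion.** The contradiction is real and should be corrected. Two classes of event, B and C above, change status with the passage followed, and the death sentence cannot be applied as written. On the reading most favorable to the sponsor, one class (B) and the death sentence still need correction.

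The consequence is limited to the adverse-event listing and the record of deaths. The study is descriptive, has no hypothesis and enrolls up to 20 subjects, and the before-and-after QT comparison does not use these events. How many events would be affected cannot be estimated from the document. The conclusion assumes only that sites work from the passages as printed.

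**What to change.** Put one identical definition in the synopsis prose, the synopsis row, Section 10 and Section 10.2. It should state expressly whether two groups are included: non-CV events hospitalized because of loading, and CV serious events without such a hospitalization. Word the Table 4 label as relatedness to the antiarrhythmic loading.

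Replace the death sentence with one that agrees with Table 3 and 10.2. The simplest version records every death with date, cause and relatedness. If the sponsor wants a narrower rule for deaths, the exception has to be stated in 10.2 as well, so that the two sections agree.

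The cost is a wording change to the protocol, one or two eCRF fields and a few extra forms.

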10.1 Definitions/Classifications

For the purposes of clinical report, event definitions align with the International Organization for Standardization standard 14155 (ISO 14155). Where the definition indicates "device", it refers to any device used in the study. This might be the device under investigation, or any market released component of the system. For the purposes of the clinical report, Medtronic will classify each adverse event according to ISO 14155:2020 definitions. The study will follow the definitions, however, is not claiming full compliance to ISO 14155:2020.

General			
Adverse Event (AE)	Untoward medical occurrence, unintended disease or injury, or untoward clinical signs (including abnormal laboratory findings) in subjects, users or other persons, whether or not related to the investigational medical device and whether anticipated or unanticipated NOTE 1: This definition includes events related to the investigational medical device or the comparator. NOTE 2: This definition includes events related to the procedures involved. NOTE 3: For users or other persons, this definition is restricted to events related to investigational medical devices.		
	(ISO 14155:2020, 3.2)		
Relatedness			

Table 3: Adverse Event Definitions

Medtronic Business Restricted

21 SEP 2022	Version 2	Page 31 of 48	Medtronic
Cardiovascular Related	An adverse event relating to the heart and the blood vessels or the circulation (e.g., atrial fibrillation, myocardial infarction, stroke, peripheral vascular disease, heart failure).		
	Seriousness		
Serious Adverse Event (SAE) (ISO 14155)	Seriousness Adverse event that led to any of the following a) death, b) serious deterioration in the health of the subject, users, or other persons as defined by one or more of the following: 1) a life-threatening illness or injury, or 2) a permanent impairment of a body structure or a body function including chronic diseases, or 3) in-patient or prolonged hospitalization, or 4) medical or surgical intervention to prevent life- threatening illness or injury, or permanent impairment to a body structure or a body function, c) foetal distress, foetal death, a congenital abnormality, or birth defect including physical or mental impairment Note 1: Planned hospitalization for a pre-existing condition, or a procedure required by the CIP, without serious deterioration in health, is not considered a serious adverse event. (ISO 14155:2020, 3.45)		
Hospitalization	A therapeutic inpatient	hospitalization (exclude	es observation unit
	emergency room and o equal to 24 hours.	utpatient visits) lasting g	greater than or

10.2 Reporting of Adverse Events

Cardiovascular-related, serious adverse events will be reported on the AE eCRF, including a description of the event, the diagnosis, the date of event onset, the date the site became aware of the event, the diagnostic tests and procedures performed, actions taken as a result of the event, and outcome of the event.

Documented pre-existing conditions are not considered AEs unless the nature or severity of the condition has worsened.

For all reportable events, initial reporting may be done by phone, fax, or on the CRF completing as much information as possible. The completed AE CRF must be submitted to Medtronic as soon as possible.

Medtronic Business Restricted

LINQ QT Study Clinical Investigation Plan				
21 SEP 2022	Version 2	Page 32 of 48		Mecttronic

For any changes in status of a previously reported adverse event (i.e., change in actions taken, change in outcome, change in relatedness), information needs to be updated on, or added to the original AE form. All AEs must be followed until the AE has been resolved, is unresolved with no further actions planned, the subject dies or exits the study, or study closure, whichever occurs first.

10.2.1 Adverse Event Classification

AEs will be classified according to the standard definitions as outlined below:

Medtronic Business Restricted

21 SEP 2022 Version 2 Page 33 of 48

What is classified?	Who classifies?	Classification Parameters	
Relatedness	Investigator	CV Related, resulting from anti-	
		arrythmia loading	
		hospitalization	
	Sponsor	Resulting from anti-arrythmia	
		loading hospitalization	
Serious	Investigator	SAE	
	Sponsor	SAE	
	Investigator	Based on presenting signs and	
Diagnosis		symptoms and other	
		supporting data	
	Sponsor	MedDRA term assigned based	
		on the data provided by	
		Investigator	

Table 4 Adverse Event Classification Responsibilities

10.2.2 Adverse Event and Device Deficiency Reporting Requirements

Regulatory reporting of AEs will be recorded and reported according to local regulatory requirements. It is the responsibility of the Investigator and the sponsor to abide by the AE reporting requirements stipulated by local law and the study site's IRB.

10.3 Product Complaint Reporting

In geographies where devices are market-released, product complaint reporting is applicable. The reporting of product complaints is not part of the clinical study and should be done in addition to the Adverse Event reporting requirements. Refer to local regulations for reporting requirements.

Product Complaint: Any written, electronic, or oral communication that alleges deficiencies related to the identity, quality, durability, reliability, safety, effectiveness, or performance of a medical device that has been placed on the market.

It is the responsibility of the investigator to report all product complaint(s) associated with a medical device distributed by Medtronic, regardless of whether they are related to intended use, misuse or abuse of the product. Reporting must be done immediately and via the regular channels for market-released products.

Medtronic Business Restricted

CONFIDENTIAL

Medtronic

LINQ QT Study Clinical Investigation Plan Image: Clinical Study Clinical Investigation Plan 21 SEP 2022 Version 2 Page 34 of 48 Mectronic

Medtronic will notify the regulatory authorities, as applicable for the following incidents immediately upon learning of them:

- Any malfunction or deterioration in the characteristics and/or performance of a device, as well as any inadequacy in the labeling or instructions for use which led or might have led to the death or serious deterioration in the state of health of a patient, user, or other person.
- Any technical or medical reason resulting in withdrawal of a device from the market by the manufacturer.

11. Statistical Design and Methods

This is a feasibility study that is exploratory in nature and with no hypothesis. Therefore, justification on sample size is not required.

11.1 General Aspects of Analysis

11.2 Analysis Execution

Analysis for the LINQ QT Study will occur when data collection has been completed. Analysis will include the primary objective. A final report will be prepared once all data collection has ended and all subjects have completed the study.

11.2.1 Primary Objective #1

The primary objective of the study is to determine if QT changes can be detected from LINQ[™]/LINQII[™] ECG that may occur during and after antiarrhythmic loading. The QT intervals before and after antiarrhythmic loading will be compared for all patients to analyze QT changes that may be caused due to antiarrhythmic drugs.

Medtronic Business Restricted

LINQ QT Study Clinical Investigation Plan Image: Clinical Study C

Analysis Methods: Descriptive summary statistics will be used for this objective.

Determination of Subjects/Data for Analysis: All subjects with data available will be included for this objective.

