21 SEP 2022

Version 2

Page 9 of 48

The Reveal LINQ[™] and LINQII[™] devices are small, leadless cardiac monitoring systems that can be inserted subcutaneously in the chest with a minimally invasive procedure and provide continuous monitoring of diagnostic parameters for up to 3 years and 4 years respectively. An algorithm [14] has been developed and validated which can continuously measure QT intervals for every beat using LINQ[™] ECG. This study is aimed at determining if QT interval changes can be detected during and after antiarrhythmic drug loading by the designed QT detection algorithm from LINQ[™] ECG.

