4.1 Objectives

4.1.1 Primary Objective

The primary objective of the study is to determine if QT changes can be detected from LINQ[™] ECG that may occur during and after antiarrhythmic loading. The QT intervals before and after antiarrhythmic loading will be compared for all patients to analyze QT changes that may be caused due to antiarrhythmic drugs.

5. Study Design

The LINQ[™] QT Study is a prospective, non-randomized, multi-center, observational, post-market clinical study. The study is expected to be conducted at up to three study sites located in the United States and will enroll up to twenty study subjects. It is anticipated that if one study site cannot enroll at least 3 subjects per month, then additional study sites will be included to meet the total enrollment target of twenty subjects.

Study subjects implanted with LINQ[™]/LINQII[™] (no more than 50% patients implanted with LINQII[™]), but no greater than 2 years for LINQ[™] or 3 years for LINQII[™], or patients who are indicated to receive a LINQ[™]/LINQII[™] implant at least 7 days prior to antiarrhythmic drug loading will be considered for enrollment in this study.

Medtronic Business Restricted

LINO OT Study Clinica	I Investigation Dian		
		I	
21 SEP 2022	Version 2	Page 10 of 48	Medtronic

Figure 1: Study Flow Diagram

Medtronic Business Restricted

LINQ QT Study Clinical Investigation Plan			
21 SEP 2022	Version 2	Page 11 of 48	Medtronic

- I. Index Antiarrhythmic Loading Event
 - 1. Subjects with LINQ[™] Implants

2. Subjects with LINQII[™] Implants

II. Follow up period

Medtronic Business Restricted

LINQ QT Study Clinical Investigation Plan			
21 SEP 2022	Version 2	Page 12 of 48	Medtronic

- III. Follow up clinic visits
 - 1. Subjects with LINQ[™] Implants

2. Subjects with LINQII[™] Implants

Medtronic Business Restricted

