11.3 Sample Size Determination

There are no sample size requirements as this is an observational study with no hypothesis for the study objective. A sample size of up to 20 enrolled subjects was selected assuming sufficient data can be collected from this cohort to explore the relationship between measured QT intervals from LINQ[™]/LINQII[™] before and after antiarrhythmic drug intake.

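### The objective asks whether QT change can be detected from the LINQ/LINQII ECG, but the visible analysis only describes device QT before and after loading and gives the scheduled 12-lead ECG no reference role

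*Protocol*

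**What the plan says.** Section 4.1.1 frames the question as one of capability: "The primary objective of the study is to determine if QT changes can be detected from" the LINQ ECG, during and after loading. Section 11.2.1 repeats this for LINQ/LINQII and names one comparison: "The QT intervals before and after antiarrhythmic loading will be compared for all patients to analyze QT changes". Its method is descriptive summary statistics, in all subjects with data.

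Section 11.2.1 does not say which QT is compared. Two other places do. Section 11.3 justifies up to 20 subjects as enough to "explore the relationship between measured QT intervals from LINQ"/LINQII before and after drug intake, and the synopsis statistics row says that LINQ/LINQII "derived data will be summarized using descriptive statistics".

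The synopsis schedule marks a 12-lead ECG at baseline, the loading event, the optional 2, 4 and 8 week visits and the 90-day visit. It gives no purpose for it.

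On accuracy, section 3.1 says that an algorithm "has been developed and validated which can continuously measure QT intervals for every beat", with a citation. It then sets the question for this study: "This study is aimed at determining if QT interval changes can be detected during and after antiarrhythmic drug loading".

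Section 11 calls the study a feasibility study, exploratory and without a hypothesis.

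**The concern.** To say that a device detects a change is to say that its reading moves when the true interval moves. A before/after summary of the device's own readings shows only that the readings moved. If loading alters the T wave so that the algorithm misplaces its end, the summary shows a shift that is partly or wholly a reading error. If the algorithm misses the change, the summary is flat and looks like no drug effect. The 12-lead ECG is the scheduled measurement that could separate these cases, and the visible analysis text does not use it.

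At stake is the wording of the conclusion. A statement that QT changes were detected would claim more than the named comparison can support. Descriptive statistics are not the problem: a descriptive comparison with a reference would answer the question.

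**Working it through.** **Reading the text.** Section 11.3 gives no alpha, power, effect size or SD for the figure of up to 20, so there is no calculation to reproduce. The check is textual.

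- 12-lead ECG: appears only in the synopsis schedule, without a role.
- Holter: section 6.1.8 says the recorder takes skin-electrode ECG as well as the device signal, but gives its use in this study as collecting LINQ ECG to measure QT. That is not a reference role.
- VitalPatch: described in the glossary and scheduled with the Holter, without an analysis role.
- Table 2, sections 8.6 to 8.10 and 11.1: no text in this copy.

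**Why device data alone cannot settle it.** The cited sotalol study in section 3.1 gives QTc 446 ± 35 ms before and 474 ± 48 ms after, a rise of 474 − 446 = 28 ms. Suppose the device reads half of any change (an assumption). It shows 0.5 × 28 = 14 ms, the same as a true 14 ms rise read correctly. No summary of the device readings separates the two.

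**What pairs with the 12-lead would show.** The documents give no correlation between before and after, no residual SD and no reading error, so all three are assumed.

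SD of the 12-lead change: SDx = √(35² + 48² − 2r·35·48) = 50.2, 43.0 and 34.3 ms for r = 0.3, 0.5 and 0.7.

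With half-size reading and residual SD 20 ms:

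- SD of (LINQ change − 12-lead change) = √((0.5·SDx)² + 20²) = 32.1, 29.4 and 26.3 ms.
- 95% half-width of the mean difference = t(n−1)·SD/√n.
- 95% half-width of the slope ≈ t(n−2)·20/(SDx·√(n−1)).

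| Pairs | Mean difference, half-width (true shortfall 14 ms) | Slope, half-width (true gap from 1 is 0.5) |
|---|---|---|
| 20 | 15.0, 13.7, 12.3 ms | 0.19, 0.22, 0.28 |
| 10 | 23.0, 21.0, 18.8 ms | 0.31, 0.36, 0.45 |

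If the residual SD is 10 to 30 ms, the mean-difference half-width runs from 9.3 to 18.3 ms with 20 pairs and 14.2 to 28.0 ms with 10. The slope half-width runs from 0.10 to 0.42 and from 0.15 to 0.67.

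**Which measure shows the error depends on its form.** Simulation, 20,000 runs per setting, 12-lead change ~ N(28, SDx), residual SD 20 ms, SDx from 34.3 to 50.2 ms:

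| Error | Pairs | Slope CI below 1 | Mean-difference CI below 0 |
|---|---|---|---|
| Half-size reading | 20 | 91% to 99% | 46% to 62% |
| Half-size reading | 10 | 58% to 84% | 23% to 33% |
| Constant 14 ms under-reading | 20 | 2% to 3% | about 84% |
| Constant 14 ms under-reading | 10 | 2% to 3% | about 50% |

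The slope shows proportional under-reading, and the mean difference shows a constant offset. Neither stands in for the other.

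**Whether pre-loading pairs can exist.** The synopsis marks MyCareLink "Daily Manual Transmissions" at Baseline, and section 6.1.7 says that the data sent by the home monitor include ECG. New implants are placed at least 7 days before loading (sections 7.3 and 8.5). Against this, "Patient Activations" and the Holter/VitalPatch row are not marked at Baseline. Pairs are plausible but not shown.

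**The case against.** The strongest reply is that this rests on absence in a copy with many empty sections. Visit procedures, recording data and general analysis are where a reference role would normally stand, and pairing rules may well be in an SAP that is not shown. A reader might infer that the study has no reference standard. The documents do not support that, and the point covers visible text only. What remains is that sections 4.1.1, 11.2.1 and 11.3 do state an objective and a comparison, and the comparison does not answer the objective.

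Second, the algorithm is said to be already validated, and detected could mean whatever the algorithm registers. The validation may make misreading less likely. But section 3.1 itself leaves detection under loading as the question here, and no visible text says that the earlier work covered it. The opposite inference, that the algorithm misreads under these drugs, has no support either.

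Third, the study has no hypothesis and no aim of showing effectiveness. This stands and limits the weight of the point.

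Fourth, the figures rest on assumptions, use QTc where the objective says QT, and take the smallest of the four changes cited in section 3.1 (28, 36, 58 and 67 ms). This also stands: they illustrate the point and do not establish it. A reader might conclude from the half-size case that the slope is the better measure, but the constant-offset case reverses that ranking.

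**Conclusion.** The concern holds for the visible text. The named comparison, a before/after description of device QT, cannot by itself determine whether QT change is detected, and the 12-lead ECG scheduled at every visit has no stated part in it. The conclusion rests on reading section 11.2.1 with section 11.3 and the synopsis statistics row as meaning device QT, and it would fall if an empty section already names a reference.

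The size is modest. It affects what the result can be said to show, not an error rate or a decision rule. Under the assumed values, 20 pairs could reveal a halved reading through the slope or a constant 14 ms offset through the mean difference. With 10 pairs the picture is uncertain. It is worth considering, with medium confidence.

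**What to change.** In section 11.2.1, beside the planned before/after summary, name the 12-lead ECGs already scheduled as the reference for QT change. For subjects with a LINQ/LINQII segment near a 12-lead both before and after loading, describe:

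- the mean difference, LINQ change minus 12-lead change, with a 95% CI;
- the slope of LINQ change on 12-lead change, with a 95% CI;
- the number of usable pairs.

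Report both measures and rank neither. The sponsor should first confirm that pre-loading pairs will exist. If they will not, or if no reference is intended, limit the objective and conclusion to describing LINQ/LINQII-measured QT before and after loading. If an empty section already names the reference, repeat it in 11.2.1.

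The cost is wording only if the pairs exist or the objective is narrowed. Otherwise a LINQ/LINQII recording near a 12-lead before loading would have to be added. The downsides are that some subjects may lack a usable pair, precision is limited at up to 20 subjects, and agreement may look less favourable than a before/after mean.
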